1.3.1.3 Clinical Studies

1.3.1.3.1 Treatment of Influenza Infection in High Risk Populations

The median duration of influenza illness in older patients (≥ 65 years) and in patients with chronic cardiac and/or respiratory disease receiving oseltamivir 75 mg twice daily (BID) for 5 days was not reduced significantly. The total duration of fever was reduced by 1 day in the oseltamivir-treated groups. In influenza-positive older people, the incidence of specified lower respiratory tract complications (mainly bronchitis) treated with antibiotics was statistically significantly lower in the oseltamivir-treated group (12% [29/250]) compared with the placebo-treated group (19% [52/268]; p = 0.0156). In influenza-positive patients with chronic cardiac and/or respiratory disease, the combined incidence of lower respiratory tract complications (mainly bronchitis) treated with antibiotics was 17 % (22/133) in the placebo-treated group and 14 % (16/118) in the oseltamivir-treated group (p = 0.5976) [9].

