9.10.3.2 Analyses of Secondary Endpoints

1) Proportion of patients positive for influenza virus titer and proportion of patients positive by RT-PCR at each time point

Only patients whose virus titer/RT-PCR predose at Visit 1 are \geq the lower limit of quantification will be included in the analyses. The summary table by each time

point will be made. The Mantel-Haenszel test at each time point will be used to compare the proportion of patients with positive virus titer/RT-PCR between S-033188 and oseltamivir/placebo with baseline symptom score ($\leq 14, \geq 15$), preexisting and worsened symptom (Yes, No), and region (Asia, North America/Europe, Southern Hemisphere) as stratification factors.

2) Change from baseline in virus titer and the amount of virus RNA (RT-PCR) at each time point

Only patients whose virus titer/RT-PCR predose at Visit 1 are \geq the lower limit of quantification will be included in the analyses. The van Elteren test will be used by each time point to compare the S-033188 with oseltamivir/placebo, where baseline symptom score ($\leq 14, \geq 15$), preexisting and worsened symptom (Yes, No), region (Asia, North America/Europe, Southern Hemisphere) will be included as stratification factors. Summary statistics will be calculated by time point and by treatment group.

3) AUC adjusted by baseline in virus titer and in the amount of virus RNA (RT-PCR)

Only patients whose virus titer/RT-PCR predose at Visit 1 are \geq the lower limit of quantification will be included in the analyses. The same statistical methods as 2) change from baseline in virus titer and the amount of virus RNA (RT-PCR) at each time point will be used. Summary statistics will be calculated by treatment group.

4) Time to cessation of viral shedding by virus titer and by RT-PCR

Only patients whose virus titer/RT-PCR predose at Visit 1 are \geq the lower limit of quantification will be included in the analyses. The same analyses as the primary endpoint will be performed.

5) Proportion of patients whose symptoms has been alleviated at each time point

The same analyses as 1) proportion of patients positive for influenza virus titer and proportion of patients positive by RT-PCR will be used.

6) Time to alleviation of symptoms

The same analyses as the primary endpoint will be performed.

 Time to improvement in the 4 systemic symptoms (headache, feverishness or chills, muscle/joint pain, and fatigue)

The same analyses as the primary endpoint will be performed.

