8) Time to improvement in the 3 respiratory symptoms (cough, nasal congestion, and sore throat)

The same analyses as the primary endpoint will be performed.

9) Time to resolution of fever

The same analyses as the primary endpoint will be performed.

10) Proportion of patients reporting normal temperature at each time point

The summary table by each time point will be made. The Mantel-Haenszel test at each time point will be used to compare the proportion of resolution of fever between S-033188 and oseltamivir/placebo with baseline symptom score (≤ 14 , ≥ 15), preexisting and worsened symptom (Yes, No), and region (Asia, North America/Europe, Southern Hemisphere) as stratification factors.

11) Body temperature at each time point

The summary table by each time point will be made. The analysis of covariance (ANCOVA) will be used by each time point to compare body temperature between S-033188 and oseltamivir/placebo, where composite symptoms score at baseline, and preexisting and worsened symptom (Yes, No), and region (Asia, North America/Europe, Southern Hemisphere) will be used as covariates.

12) Time to improvement of each influenza symptom

The same analyses as the primary endpoint will be done. Patients whose symptoms at baseline are assessed as 0 (None), 1 (Mild), 2 (Moderate) but preexisting and not worsened, or 3 (severe) but preexisting and not worsened will be excluded from the analysis.

13) Time to return to preinfluenza health status

The same analyses as the primary endpoint will be performed.

14) Requirement for systemic antibiotics for infections secondary to influenza infection

A summary table will be created. The Fisher's exact test will be used to compare the percentage of patients who used systemic antibiotics for infections secondary to influenza infection between S-033188 and oseltamivir/placebo.

15) Incidence of influenza-related complications (hospitalization, death, sinusitis, bronchitis, otitis media, and radiologically-confirmed pneumonia)

A summary table will be created. Fisher's exact test will be used to compare the incidence between S-033188 and oseltamivir/placebo.

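### Antibiotic use and complications are compared by an unstratified Fisher's exact test while the other binary secondary endpoints use stratified Mantel-Haenszel: valid, but about 2 to 6 points less powerful

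*Protocol*

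**What the plan says.** Protocol 9.10.3.2 sets the tests for the binary secondary endpoints:

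- Item 14, systemic antibiotics: Fisher's "exact test will be used to compare the percentage of patients who used systemic antibiotics for infections secondary to influenza infection", S-033188 against oseltamivir and placebo. No stratification factor is named.
- Item 15, influenza-related complications: Fisher's "exact test will be used to compare the incidence between S-033188 and oseltamivir/placebo". Again no factor is named.
- Item 1, virus positivity: "The Mantel-Haenszel test at each time point will be used to compare the proportion of patients with positive virus titer/RT-PCR between" the groups, stratified by baseline symptom score, preexisting and worsened symptom, and region.
- Item 5, symptoms alleviated: "The same analyses as 1) proportion of patients positive for influenza virus titer and proportion of patients positive by RT-PCR will be used".
- Item 10, normal temperature: "The Mantel-Haenszel test at each time point will be used to compare the proportion of resolution of fever", with the same three factors.

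Section 5.4 stratifies randomization by these three factors and by weight. The primary analysis (9.10.3.1.1) uses the same three factors. The protocol gives no reason for treating items 14 and 15 differently. Section 9.10.2 defines item 15 as the percentage of patients with each complication separately; it defines no summary of any complication.

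**The concern.** The trial enrols patients because they are at high risk of complications, and section 3.2.2 bases its placebo rationale partly on the lack of good randomized evidence about complications. Items 14 and 15 bear on that gap most directly, yet among the binary secondary endpoints they alone get an unstratified test. Fisher's test conditions on the total number of events. Its attainable significance levels are therefore discrete, and the true error rate falls below the nominal 5%. The stratum data are already collected. What is at stake is some power for two clinically important secondary comparisons.

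**Working it through.** **Inputs.** 395 infected patients per arm, allocation 1:1:1 (9.2, 5.4). Two-sided 5% level (9.1). Strata: 2 x 2 x 3 = 12. Background rates from section 1.3.1.3.1 for antibiotic-treated lower respiratory complications: in older patients 29/250 = 11.6% on oseltamivir, "compared with the placebo-treated group (19% [52/268]; p = 0.0156" (52/268 = 19.4%); in chronic cardiac and/or respiratory disease 16/118 = 13.6% against 22/133 = 16.5% on placebo. The protocol gives no event rate or power for items 14 and 15, so all other rates below are assumptions.

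**Protocol figures reproduced.** The generalized Wilcoxon test with exponential times, medians of 150 and 114 hours and censoring at 336 hours has 90.01% power at 395 per arm. 395/0.55 = 718.2, rounded up to 719, and 719 x 3 = 2157. Fisher's test on the two background tables gives p = 0.0156 and 0.5976, as printed.

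**Exact comparison, no strata.** With a and b events in two arms of n = 395 and m = a + b, the uncorrected Mantel-Haenszel statistic for one stratum is

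X² = (a − b)²(2n − 1) / [m(2n − m)], rejecting at X² ≥ 3.841.

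The rejection probability of either test is the sum, over all (a, b) that it rejects, of Bin(a; 395, p1) x Bin(b; 395, p2).

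| True rates | Fisher | Uncorrected statistic |
|---|---|---|
| 5% in both (size) | 3.4% | 4.8% |
| 10% in both (size) | 3.8% | 5.0% |
| 19.4% in both (size) | 4.1% | 5.0% |
| 19.4% vs 11.6% (cited) | 84.0% | 86.2% |
| 16.5% vs 13.6% (cited) | 18.0% | 20.6% |
| 10% vs 5% (assumed) | 73.1% | 77.0% |
| 5% vs 2.5% (assumed) | 39.3% | 45.6% |

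The differences in power are 2.2, 2.6, 3.9 and 6.3 points.

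Hand check of the first power row by the normal approximation: (0.078 x √395 − 1.96 x √(2 x 0.155 x 0.845)) / √(0.194 x 0.806 + 0.116 x 0.884) = (1.550 − 1.003)/0.509 = 1.075, which gives 85.9%, close to 86.2%.

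**With 12 strata.** Simulation with assumed stratum sizes (396 per arm after rounding) and three assumed spreads of risk between strata: none; 4.9% to 22.0%; and 2.1% to 38.6% (spreads shown for an overall rate of 10%). Power in each cell is Fisher / Mantel-Haenszel uncorrected / Mantel-Haenszel with continuity correction.

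| Overall rates | Equal risk | Moderate spread | Wide spread |
|---|---|---|---|
| 19.4% vs 11.6% | 83.8 / 86.0 / 83.6 | 84.5 / 87.2 / 85.0 | 85.5 / 89.6 / 87.4 |
| 10% vs 5% | 73.3 / 77.2 / 72.5 | 73.4 / 77.6 / 73.3 | 73.8 / 79.2 / 74.9 |
| 5% vs 2.5% | 40.1 / 46.4 / 38.9 | 39.3 / 45.8 / 38.4 | 39.3 / 47.1 / 39.5 |

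Under the null, at true rates of 3% to 17%, the uncorrected stratified test stayed close to 5% and Fisher's ran at 2.9% to 4.1%.

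**Sparse events.** At a true rate of 1% (equal risk in all strata), on average 6.8 of the 12 strata hold no event in either arm. At 0.5% it is 8.8 of 12.

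**The case against.** The main defence is that nothing here is an error. Fisher's test does not inflate type I error, the synopsis lists both tests among the planned procedures, and section 9.1 lets the SAP change an analysis if it gives the reason. All of that stands; the point is an improvement in efficiency.

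Three stronger readings are tempting, and the document does not support them:

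- **That the loss comes mainly from discarding the strata.** With equal risk across strata, the continuity-corrected stratified test has about the same power as Fisher's (83.6% against 83.8%). Most of the loss is therefore Fisher's discreteness. Stratifying adds to the gain only if risk differs between strata, and the protocol gives no information on that.
- **That the protocol itself shows these events to be common.** The cited placebo rates would mean 0.165 x 395 = 65 to 0.194 x 395 = 77 events in an arm. They describe a related but different outcome in two subgroups: patients aged 65 or older, and patients with chronic cardiac and/or respiratory disease. This trial enrols from age 12 across many other risk groups.
- **That all of item 15 should move to Mantel-Haenszel.** Item 15 is defined complication by complication. Death, hospitalization and radiologically confirmed pneumonia may well be sparse, and Fisher's test is a sound choice for sparse components.

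**Conclusion.** The point holds as a minor one. For item 14 and for any complication that proves reasonably common, the planned test spends less than its 5% and gives up about 2 to 6 points of power against the uncorrected Mantel-Haenszel statistic. At the cited 19.4% and 11.6%, the simulated gain from the stratified test was 2.2 points with equal risk across strata (86.0 − 83.8) and 4.1 with the widest assumed spread (89.6 − 85.5).

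The exact results rest on 395 per arm and on the event rates shown, of which only the two background pairs come from the protocol. The stratified results also rest on assumed stratum sizes and risks. The sample size does not depend on these endpoints, and the only type I error hierarchy described covers the primary endpoint (9.1, 9.10.3.1.2). No primary conclusion changes.

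**What to change.** In 9.10.3.2:

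- Item 14: use the Mantel-Haenszel test of item 1, stratified by baseline symptom score, preexisting and worsened symptom, and region. State that no continuity correction is applied, since the correction removes most or all of the gain.
- Item 15: use the same test for each complication that is not sparse, and keep Fisher's exact test for sparse components such as death. Fix the rule for sparse before unblinding, for example as a minimum number of events pooled over arms.
- If a summary of any complication is wanted, define it in 9.10.2 and test it in the same way.

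If Fisher's test is kept throughout, a sentence giving the reason would be enough.

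The cost is a few lines of text and one procedure call on data already collected. The downside is small: strata without events contribute nothing, which is why the sparse components stay with Fisher's test.

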9.11 Safety Analyses

The safety population will be used for safety analyses.

9.11.1 Adverse Events

Adverse events will be classified by system organ class and preferred term using Medical Dictionary for Regulatory Activities (MedDRA). Of reported AEs on the eCRF, AEs reported after the initial dose of randomized study drug will be used for safety analyses.

The number of patients who experienced at least 1 AE, deaths, other SAEs, and AEs leading to withdrawal will be counted for each treatment group. The incidences and their 95% CI will be calculated by using the Clopper-Pearson method. The number of those

AEs, which are counted by cases reported, also will be presented. Treatment-related AEs will be summarized in the same manner as AEs described above.

The number and percentage of patients who experienced AEs by MedDRA system organ class (SOC) and preferred term (PT) will be presented for each treatment group. The summary for timing of onset, severity, action taken with the study drug, and outcome will be presented by SOC and PT. All AEs, including those occurring prior to the initiation of the study treatment, will be listed.

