In addition, a secondary efficacy analysis will be performed on the comparison of the primary endpoint by comparing between S-033188 and oseltamivir using the same statistical methods as used for the primary efficacy analysis. Together with the primary efficacy analysis, this comparison will be conducted in a hierarchical manner so as to maintain control of overall type I error. For Japan, control of overall type I error is not required for the secondary efficacy analysis of primary endpoint.

Other Secondary Efficacy Analyses:

The following analytical procedures will be applied to the various secondary efficacy variables: stratified generalized Wilcoxon test, analysis of covariance (ANCOVA), van Elteren test, Mantel-Haenszel test, and Fisher's exact test.

Safety Analyses:

For AEs and treatment-related AEs, the number of events and patients with AEs/treatment-related AEs will be counted for each treatment group. The numbers of events and patients with AEs/treatment-related AEs will be counted by system organ class and preferred term for each treatment group.

Descriptive statistics (number of patients, mean, standard deviation, minimum, median, and maximum) for quantitative data obtained at each time point will be calculated for each treatment group for vital sign measurements, ECGs, and laboratory values. For qualitative data, the frequency of each category at each time point will be summarized.

Study Duration:

Study duration in individual patients: 22 days

Planned study duration for the study: CPI

Date of Original: 05 August 2016

Date of Latest Amendment: 31 October 2016 (Amendment 2)

TABLE OF CONTENTS

SYNOPSIS	3
TABLE OF CONTENTS	10
LIST OF IN-TEXT TABLES	15
LIST OF IN-TEXT FIGURES	15
LIST OF ABBREVIATIONS AND DEFINITIONS OF TERMS	16
1. INTRODUCTION	19
1.1 Nonclinical Studies	20
1.1.1 Pharmacology	20
1.1.2 Safety	20
1.1.3 Pharmacokinetics	21
1.2 Clinical Studies	22
1.2.1 Single-ascending Dose Study (Study 1510T0811)	22
1.2.2 Relative Bioavailability and Food Effect Study (Study 1512T08)	13)23
1.2.3 Drug-Drug Interaction Study with Midazolam (Study 1519T081	4)23
1.2.4 Drug-drug Interaction Study with Itraconazole (Study 1520T081	5)24
1.2.5 Thorough QT/QTc Study (Study 1527T0816)	24

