2.4 Safety Objectives

- To compare the safety and tolerability of a single dose of S-033188 with placebo
- To compare the safety and tolerability of a single dose of S-033188 with oseltamivir 75 mg BID for 5 days
- To compare the frequency of adverse events in patients with influenza of a single dose of S-033188 with oseltamivir 75 mg BID for 5 days and with placebo

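### The safety objectives are comparative, but Section 9.11.1 plans only per-group adverse event incidences with one-sample intervals and no between-arm estimate

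*Protocol*

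**What the plan says.** Protocol Section 2.4, repeated in the synopsis, lists three safety objectives, all comparative. One is "To compare the safety and tolerability of a single dose of S-033188 with placebo", the second makes the same comparison with oseltamivir, and the third names the quantity, "To compare the frequency of adverse events in patients with influenza of a single dose of S-033188", against both controls.

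Section 9.11.1 sets out the AE analysis. Patients with at least one AE, deaths, other SAEs and "AEs leading to withdrawal will be counted for each treatment group". Then: "The incidences and their 95% CI will be calculated by using the Clopper-Pearson method". Treatment-related AEs are handled the same way. Coded terms are tabulated in each arm as patient counts with percentages. The synopsis likewise says "the number of events and patients with AEs/treatment-related AEs will be counted for each treatment group". Vital signs, laboratory values and ECG findings (Sections 9.11.2 to 9.11.4) are also summarised by group.

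Between-arm methods are named elsewhere. For influenza-related complications, item 15 of Section 9.10.3.2 says "Fisher's exact test will be used to compare the incidence between S-033188 and oseltamivir/placebo"; antibiotic use is treated the same way in item 14. Section 9.13.1 names a Wilcoxon rank sum test of S-033188 against placebo for the antibody titer ratio.

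**The concern.** A Clopper-Pearson interval describes the uncertainty of one arm's incidence. It does not estimate how much more or less frequent AEs are on S-033188 than on a control, which is what the objectives ask. The protocol names a between-arm method for other binary outcomes, but for overall AE incidence the only method it names is a one-sample one.

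The stake is interpretive. The introduction motivates the drug partly by tolerability relative to oral neuraminidase inhibitors, so the contrast with oseltamivir is likely to be drawn. A reader given only two one-arm intervals has no planned estimate of that contrast, and two such intervals are a poor substitute for an interval for the difference.

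**Working it through.** **Inputs.**
- 719 randomized per arm, 2157 in total (Section 9.2). This approximates the safety population, which is everyone randomized who takes at least one dose (Section 9.3).
- 95% intervals, matching Section 9.11.1.
- AE incidences: none are given in the protocol. Reference rates of 1% to 30% are assumptions.

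**The plan's own figures.** The protocol states no figure for the AE comparison. Its design figures reproduce. The Gehan generalized Wilcoxon test with exponential times, medians of 114 and 150 hours, censoring at 336 hours and 395 per arm gives 90.0% power, and 395 is the smallest number per arm that reaches 90%. Inflation for a 55% RT-PCR-positive rate gives 395/0.55 = 718.2, rounded up to 719, and 3 x 719 = 2157.

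**Illustration at one assumed pair.** Take 216/719 = 30.0% and 180/719 = 25.0%.

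1. Clopper-Pearson limits are the 2.5% quantile of Beta(x, n-x+1) and the 97.5% quantile of Beta(x+1, n-x). They are 26.7-33.5% and 21.9-28.4%. The intervals overlap, since 26.7 < 28.4.
2. Newcombe's interval for the difference d = p1 - p2 uses the Wilson limits (l, u) of each arm: d - sqrt[(p1-l1)^2 + (u2-p2)^2] to d + sqrt[(u1-p1)^2 + (p2-l2)^2]. The Wilson limits are 26.80-33.49% and 22.01-28.33%, with p1 = 30.04%, p2 = 25.03% and d = 5.01 points.
   - Lower: 5.01 - sqrt(3.24^2 + 3.29^2) = 5.01 - 4.62 = 0.4.
   - Upper: 5.01 + sqrt(3.45^2 + 3.03^2) = 5.01 + 4.59 = 9.6.
3. Fisher's exact test on the same table gives p = 0.039.

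The same counts therefore give overlapping one-arm intervals and a difference interval that excludes zero.

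**Range of assumed reference rates, 719 per arm.** Smallest excess over the reference arm, in percentage points:

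| Reference rate | Newcombe 95% CI excludes 0 | One-arm Clopper-Pearson intervals no longer overlap |
|---|---|---|
| 1% | 1.4 | 2.2 |
| 5% | 2.6 | 3.9 |
| 10% | 3.3 | 5.0 |
| 25% | 4.7 | 6.8 |
| 30% | 4.9 | 7.1 |

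At the ends of the range the ratios are 2.2/1.4 = 1.6 and 7.1/4.9 = 1.4. Separation of the one-arm intervals corresponds to a Fisher p of about 0.005.

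**The case against.** **Left to the SAP.** Section 9.1 leaves detailed methods to an SAP that is not shown here, and that SAP could add a contrast; Section 9.11.1 does not rule one out. This stands as a limit on the point. However, Section 9.1 also says the SAP will follow this part of the protocol. Section 9.11.1 names an interval method, whereas Sections 9.13.2, 9.13.3, 9.13.4.2 and 9.13.5 hand their methods over explicitly. The mismatch between objective and stated method is visible in the protocol itself.

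**No overlap rule exists.** A reader might infer that the plan will judge AE differences by whether the one-arm intervals overlap, and that real differences would then be reported as comparable. The protocol does not support that: nothing in Section 9.11 prescribes such a rule. The non-overlap column above shows only why one-arm intervals do not stand in for an interval for the difference. It is not the error rate of a planned procedure. The per-group counts will be reported, so a reader could also calculate a difference from them.

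**The objective is partly met.** A reader might also infer that nothing planned addresses the safety objectives. That goes too far. Side-by-side incidences in randomized, blinded arms are a descriptive comparison. Hospitalization, death, sinusitis, bronchitis, otitis media and radiologically confirmed pneumonia, recorded as AEs under Section 9.10.2, do get Fisher's exact test against both controls. But that test covers a short list of influenza complications as an efficacy endpoint, for which Section 9.10 makes the ITTI population primary, and it gives a p-value rather than an estimate with an interval.

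**Descriptive safety reporting is common.** The trial sets no safety hypothesis or margin and is not sized for safety. This is correct, and it keeps the point minor.

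**Conclusion.** The point holds in a limited form. The objectives are to compare AE frequency between S-033188 and each control, while Section 9.11.1 specifies per-group incidences with one-sample intervals. Outside the Fisher test on complications, the protocol plans no between-arm AE estimate with uncertainty.

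The size is illustrative and rests on two assumptions: about 719 dosed patients per arm, and reference incidences between 1% and 30%. On these, an interval for the difference resolves excesses of about 1.4 to 4.9 points, against 2.2 to 7.1 points for separation of the one-arm intervals. The finding is minor and does not touch the primary analysis, type I error control or the sample size.

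**What to change.** In Section 9.11.1, or in the SAP text that implements it, add for the safety population the difference in incidence, S-033188 minus placebo and S-033188 minus oseltamivir, each with a 95% CI by the Newcombe or Miettinen-Nurminen method. Do this for any AE, treatment-related AEs, SAEs and AEs leading to withdrawal. Label the intervals descriptive and unadjusted for multiplicity, and keep the per-group Clopper-Pearson intervals.

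The cost is a sentence of text and two extra table columns; no new data are needed. The downside is that unadjusted intervals may be over-read, which the label is meant to limit. Rewording the objectives as descriptive would also remove the mismatch, but would leave the contrast with each control without an interval.
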